9. SAFETY EVALUATION

9.1 Overview of Safety Analysis Methods

All safety analyses will be carried out using the Safety population. The following assessments will be used to evaluate the safety of propranolol for participants with TMD:

- Adverse events (AEs)
- Vital signs
- Unanticipated Problems

9.2 Adverse Events

All AEs will be coded to a system organ class (SOC) and preferred term (PT) using the *Medical Dictionary for Regulatory Activities* (MedDRA) version 18.0. All tabular AE summaries will be for treatment-emergent AEs (TEAEs). TEAEs will be defined as those AEs with an onset on or after the date of first dose of study drug (study visit 1: V1). If an AE was recorded prior to the first dose of study drug and there was an increase in its severity, the AE will be considered a TEAE. All other AEs will be classified as non-treatment-emergent. Non-treatment-emergent AEs will be flagged in all AE data listings.

An overall summary table will be developed to report the number of events and the incidence of participants having at least one event in the following categories:

TEAEs

Version 3.0 Page 18 of 25

- TEAEs indicated as serious (SAEs)
- TEAEs that lead to study drug discontinuation
- TEAEs with an outcome of death
- TEAEs that were reported as having a definite, probable, or possible relation to study drug
- TEAEs reported as having a severity rating of severe

In addition, a summary table of TEAEs classified by system organ class (SOC) and preferred term (PT) will be provided for each of the following:

- TEAEs
- TEAEs by maximum severity
- TEAEs by relationship to study drug
- TEAEs by week of treatment

The summary of all TEAEs will present both the number of TEAEs and the incidence of TEAEs by severity, and relationship to study drug. When reporting the number of TEAEs, if the same TEAE occurs for a patient on multiple occasions, the event will be counted once for each occurrence. When reporting the incidence, a patient will only be counted once if they ever experience an event within the SOC and ever experience the individual PT.

If for any TEAE (system organ class or preferred term) the incidence rate is 5% or more in either treatment arm then a logistic regression will be performed and descriptive p-values of treatment arm differences will be reported.

For the summary of TEAEs by severity, if the severity of the TEAE is not reported, then the severity of the AE will be counted as severe. If the same TEAE occurs for a patient on multiple occasions, the TEAE will be categorized according to the highest severity rating for that TEAE in that patient. For the summary of TEAEs by relationship to study drug, if the relationship is missing, it will be counted as definite/certain. If the same TEAE occurs for a patient on multiple occasions, the TEAE will be categorized according to the closest relationship to study drug reported for that TEAE in that patient.

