2. PROTOCOL SUMMARY

A total of 200 participants aged 18 to 65 years with chronic temporomandibular disorder (TMD), at three clinic sites, will be randomized in a 1:1 ratio to propranolol or placebo in a parallel-group, masked clinical trial. Participants will attend 6 clinic visits over a period of 12 to 15 weeks.

Potential participants will be prescreened by telephone or at a clinic visit. During the Screening and Baseline Visit, participants will be consented, evaluated for eligibility, and assessed for baseline characteristics. Baseline procedures will include clinical tests and examinations and the administration of questionnaires.

At the Randomization and Titration Visit, participants will be randomized to propranolol or placebo and will begin a 10-week drug treatment phase that is divided into 1 week of drug titration, 8 weeks of drug maintenance, and 1 week of drug tapering. During treatment, many of the baseline assessments will be repeated. The final study visit will occur 1 week after drug tapering ends.

The primary endpoint will be a weekly pain index derived from a daily symptom diary. Secondary endpoints will be additional ratings of clinical pain; examiner assessments of experimental pain sensitivity; participant ratings of physical function, emotional function, and global improvement; occurrence of symptoms and adverse events; and use of rescue medications. DNA analyses will be conducted to identify polymorphisms in the gene that encodes catechol-O-methyltransferase (COMT), an enzyme that metabolizes catecholamines such as epinephrine, norepinephrine, and dopamine and is associated with responses to pain.

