2.6 Sample Size Determination

This study plans to randomize 200 participants, which will provide 94% power (alpha = 0.05) to detect a difference between a 27% reduction in pain intensity in the propranolol arm and a 9% reduction in the placebo arm (primary hypothesis). Assuming haplotype distributions and within-haplotype treatment effects that are similar to those observed in the pilot study, the same sample size would provide 61% power (alpha = 0.05) to detect an interaction between haplotype and treatment group (secondary hypothesis).

Power calculations were made using the GLMPOWER procedure in SAS, which assumes a data structure of one observation per person. This is a simplification of the situation that will occur with the linear mixed model, described in Section 10.4.1, where efficacy will be evaluated using a data structure where most participants will have three observations per person. The simplified power calculations are shown here because conventional software for power calculations does not deal with the more complex situation of linear mixed models.

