- For continuous variables, summary statistics will consist of the number of patients, mean, median, standard error of the mean (SE), minimum, and maximum values. The summary statistic n will be the number of patients with non-missing values. All means and medians will be reported to one more significant digit than the values being analyzed. Standard errors will be reported to two more significant digits than the values being analyzed. The minimum and maximum will be reported to the same number of significant digits as the values being analyzed.
- For tests of hypothesis of treatment group differences, the associated P-value will be reported.
- Version 9.4 or later of the SAS® software package will be used to produce all summaries, listings, statistical analyses, and graphical presentations.

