4.3 Safety Population

Section 11.3.3 of the protocol defines the safety population as follows:

The safety sample will include all randomized participants who received at least one dose of study medication. Participants in the safety sample will be analyzed with the treatment group according to the medication they actually received, regardless of their randomized assignment.

All adverse events (AEs) will be recorded on a case report form regardless of study population. For safety analyses, all AEs will be provided in listings, but only treatment emergent adverse events (TEAEs) within the safety population will be reported in summary tables.

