8.3 Analysis Methods

The ITT population will be used in all analyses unless otherwise stated. The alpha level for determining significance will be set to 0.05 for all inference tests. The mixed models analyses described below automatically adjust for missing values; there will be no further imputation or adjustments for missing values. During the analysis of the primary hypothesis, treatment allocation will be masked (i.e., groups will be labeled A and B) during the statistical programming and unmasked only after the statistical programming code has been finalized.

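### SAP 9.2 names no test statistic and no zero-event rule for its adverse-event logistic regression, so the same one-arm-only event can be reported with P of about 0.99 or P below 0.01.

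*SAP*

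**What the plan says.** The rule in SAP 9.2 applies to every TEAE at both levels of coding: if "the incidence rate is 5% or more in either treatment arm then a logistic regression will be performed and descriptive p-values" of the arm comparison follow. The outcome is binary, because for incidence "a patient will only be counted once if they ever experience an event within the SOC", and likewise once per preferred term.

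The trigger looks at either arm and sets no minimum in the other. Section 9 gives no covariates, no test statistic (Wald, score or likelihood ratio), no exact or penalised method, and no rule for zero cells or non-convergence. SAP Section 3 names only the software, SAS 9.4 or later: this "software package will be used to produce all summaries, listings, statistical analyses, and graphical presentations".

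On the analysis set, SAP 4.3 says "The safety sample will include all randomized participants who received at least one dose of study medication". Its size is not given. SAP 2.6 says "This study plans to randomize 200 participants", and SAP Section 2 says they "will be randomized in a 1:1 ratio to propranolol or placebo".

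SAP 8.3, on efficacy, says "The alpha level for determining significance will be set to 0.05 for all inference tests". SAP 9.2 does not apply that threshold to adverse events; it calls their P-values descriptive.

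**The concern.** At 100 per arm, 5 events in one arm and none in the other meets the trigger. A logistic model with a treatment term then has no finite maximum-likelihood estimate (separation). The software stops at a large log odds ratio with an enormous standard error. A Wald P-value, which is what is commonly read off beside a logistic coefficient, is then close to 1 however many events occurred.

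At stake is how the safety table reads. The most one-sided events could carry P-values suggesting no difference, while weaker imbalances carry small ones. This is the only between-arm test in SAP Section 9, and SAP 2.1.2 includes the occurrence of symptoms and adverse events in a secondary objective. Elsewhere the SAP does plan for zeros: for days on rescue medication, SAP 8.3.2 gives a log(x+1) transformation and a fallback model. SAP 9.2 has no equivalent.

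**Working it through.** The documents give no P-value or power for this comparison, so there is no figure of theirs to reproduce. The only stated number is the 5% trigger.

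**Inputs.** 200 randomised 1:1 gives 200/2 = 100 per arm. The size of the safety population is an assumption, taken as 100 per arm with a range of 90 to 100. Treatment is the only model term, since no covariates are listed. Tests are two-sided, since sidedness is not stated. The trigger at 100 per arm is 0.05 × 100 = 5 events.

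**Wald test, 6 v 0.** Newton-Raphson with a 1e-8 relative gradient criterion stops at a log odds ratio of 17.45 with standard error 2437.8. Then z = 17.45/2437.8 = 0.007 and P = 0.994. Another program with a different stopping rule gives 21.81 with standard error about 13,101 and P = 0.999. Estimate and standard error reflect the stopping rule, not the data.

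**Likelihood-ratio test, same model, 6 v 0.**
- With a treatment effect: 6 ln(0.06) + 94 ln(0.94) = −22.697.
- Without: 6 ln(0.03) + 194 ln(0.97) = −26.948.
- Statistic: 2 × (26.948 − 22.697) = 8.50 on 1 degree of freedom, P = 0.0035. This likelihood has a finite limit, so separation does not break the test.

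**Fisher's exact test, x v 0.** With equal arms, P = 2 × C(100, x)/C(200, x). For x = 5 this is 2 × (100·99·98·97·96)/(200·199·198·197·196) = 2 × 0.0297 = 0.059. For x = 6, multiply by 95/195: 0.029.

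**Two-sided P-values at 100 per arm**

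| Events | Wald | Likelihood ratio | Score | Fisher | Firth, Wald | Firth, penalised LR |
|---|---|---|---|---|---|---|
| 5 v 0 | 0.994 | 0.0079 | 0.0235 | 0.059 | 0.099 | 0.025 |
| 6 v 0 | 0.994 | 0.0035 | 0.0129 | 0.029 | 0.075 | 0.012 |
| 7 v 0 | 0.994 | 0.0016 | 0.0071 | 0.014 | 0.058 | 0.006 |
| 8 v 0 | 0.994 | 0.0007 | 0.0039 | 0.007 | 0.046 | 0.003 |
| 10 v 0 | 0.994 | 0.0001 | 0.0012 | 0.0015 | 0.030 | 0.0006 |

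At 90 or 95 per arm every entry agrees to within 0.001.

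**One event in the other arm, 8 v 1.** Log odds ratio = ln[(8 × 99)/(92 × 1)] = 2.153. Standard error = √(1/8 + 1/92 + 1/1 + 1/99) = 1.070. Then z = 2.01 and Wald P = 0.044; Fisher's P is 0.035. The gross failure has gone, but the ordering is perverse: by Wald, 8 v 1 gives 0.044 and 10 v 0 gives 0.994, whereas Fisher gives 0.035 and 0.0015.

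**Chance of an empty placebo arm.** For a true placebo rate p, this is (1 − p)^100. For p = 1%, 2% and 3% it is 37%, 13% and 5% per term. These rates are assumed; the documents give none.

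**The case against.** A reader might infer that the SAP mandates ordinary maximum likelihood with a Wald test, so that any one-arm-only event must be reported with P near 1. The text does not support that. It asks for a logistic regression and leaves the method and test statistic open. An analyst who took the likelihood-ratio P-value from the same fit would comply and would report 0.0079 at 5 v 0. It would also be wrong to say that an exact test is always significant where Wald fails: at the trigger itself Fisher gives 0.059, and the contrast at 0.05 begins at 6 v 0.

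A reader might also infer that a real safety signal would be lost. The documents do not support that either. The P-values are labelled descriptive, no stopping or decision rule uses them, and SAP 9.2 tabulates counts and incidence by system organ class and preferred term. SAP 9.3 adds tables and listings of deaths, serious events and discontinuations. A row showing 8 v 0 would be in plain view.

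Nor are 37%, 13% and 5% the chance of the problem. They are the chance of no placebo events; at least 5 events on propranolol are needed as well. An empty placebo arm is also less plausible for several expected effects. Protocol 8.1 lists common symptoms such as dizziness, fatigue and nausea, the Symptom Inventory asks about expected effects in both arms at every visit, and Protocol 2.1.4 reports similar rates of nausea, diarrhea and fatigue on propranolol and placebo in the pilot (a lower dose, for one week).

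All of this stands and limits the point. It does not remove it: the plan permits 0.99 or 0.0035 on identical data at 6 v 0, and a descriptive P-value should still describe the data. Adding covariates such as site would not cure the separation.

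**Conclusion.** The concern holds as a gap in specification. With one arm at zero, the result under SAP 9.2 depends on a choice that the SAP does not make, and the Wald choice gives about 0.99 regardless of the count. Any odds ratio or Wald interval taken from such a fit is unusable whichever P-value is quoted. The consequence is confined to the reading of the safety table. No trial decision and no efficacy result depends on it.

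This rests on about 100 per arm in the safety population (90 to 100 makes no material difference), a model with treatment only, and two-sided tests. How often it would arise cannot be worked out from the documents.

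**What to change.** In SAP 9.2, for each system organ class and preferred term that meets the 5% trigger, report Fisher's exact P-value and a risk difference with a score or exact 95% interval. At minimum, do so whenever an arm has zero or very few events, since tables without sparse cells fit normally.

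If a model is preferred, name exact logistic regression, or Firth logistic regression with a penalised likelihood-ratio P-value and profile-likelihood limits. Firth with a Wald P-value is not enough: it gives 0.075 at 6 v 0 and falls below 0.05 only from 8 v 0.

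The cost is a sentence in the SAP and standard software options. Data collection, sample size and the primary analysis are untouched. The downside is that Fisher's test is slightly conservative with small counts.

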9.3 Deaths, Serious Adverse Events, and Other Significant Adverse Events

In addition to these summary tables, the incidence of adverse events leading to death, the incidence of SAEs, and incidence of TEAEs that led to study drug being discontinued will be presented in summary tables and listings. The summary listings will provide all of the information reported for that AE and will include the number of days from date of first dose to date of the occurrence of the AE.

9.4 Vital Signs and Other Observations Related to Safety

Listings will include all participant vital signs and any other comments as provided by the examining clinician. Vital signs statistics will be summarized in table form by treatment group and study visit. These tables will include summary statistics appropriate for variable type as listed in Section 3.

Version 3.0 Page 19 of 25

9.5 Unanticipated Problems

Unanticipated problems will be included in the listings.

Version 3.0 Page 20 of 25

10. INTERIM ANALYSES AND DATA MONITORING

No interim analyses have been planned.

[figure not shown]
11. CHANGES TO THE ANALYSES PLANNED IN THE PROTOCOL

No changes to the analyses planned in the protocol have been made.

Version 3.0 Page 21 of 25

12. APPENDICES

12.1 Study Schematic

Version 3.0 Page 22 of 25

12.2 Schedule of Events

Study Phase:	Pre-screening ^a	Screening and Baseline	Randomization and Treatment (1 week titration, 8 weeks maintenance, and 1 week taper)				Follow-Up
Clinic Visit:		V0	V1 ^b	V2	V3	V4	V5
Study Day:	≤ 28 days prior to V0	7 to 21 days prior to V1	0	7 (+ 3)	35 (± 7)	63 (+ 6)	77 (+ 7)
Procedure							
Contact Information	X						
Prescreening Interview Script	X						
Informed Consent ^c		X					
Eligibility Review	X	x	X				
AUDIT Questionnaire		X					
Smoking Questionnaire		X					X
Alcohol Consumption per week			X	x	X	X	X
Demographic Information		x					
Medical History and Review	X	X	X	X	X	X	X
Concomitant Medications		x	X	X	X	X	X
Concomitant Therapies		x	X	x	X	X	X
Dispense New Daily Symptom Diaries		x	X	X	X	X	
Adverse Event Review			X	X	X	X	X
Collect Daily Symptom Diaries			X	X	X	X	X
Assess Compliance with Daily Symptom Diaries			X	X	X	X	X
Collect Confidence in Treatment Outcome			X				
Randomization			X				
Dispense Study Drug			$\mathbf{x}^{\mathbf{d}}$	X	х	x	
Collect Study Drug Container(s)				X	X	X	X
Assess Compliance with Study Drug				X	X	X	X
Clinical Examinations and Tests							
Physical Measurements		X					

Study Phase	: Pre-screening ^a	Screening and Baseline	Randomization and Treatment (1 week titration, 8 weeks maintenance, and 1 week taper)				Follow-Up
Clinic Visit	:	V0	V1 ^b	V2	V3	V4	V5
Study Day	$ \begin{array}{ c c c c c c c c c c c c c c c c c c c$	7 to 21 days prior to V1	0	7 (+ 3)	35 (± 7)	63 (+ 6)	77 (+ 7)
Vital Signs		X	X	X	X	X	X
Urine Pregnancy Test (females)		x	X	X	X	X	x
Manual Tender Point Exam		X					
TMD Examination		X			X	X	
Heat and Pressure Pain Tests		x			X	X	
12-Lead ECG		x					
Blood Draw			X			X	
Schedule Next Visit	X	x	X	х	X	X	
Outcome Measure Questionnaires							
Symptom Inventory		X	X	X	X	X	X
Fibromyalgia Questionnaire		x					
Headache Questionnaire ^e			X				
SF-McGill Pain Questionnaire		X		Х	X	X	х
Graded Chronic Pain Scale ^e			X		X	X	
SF-12 Health Survey v2 ^e			X		X	X	
Jaw Functional Limitation Scale ^e			Х		Х	Х	
Perceived Stress Scale ^e			X		X	X	
Hospital Anxiety and Depression Scale ^e			Х		х	х	
Pittsburgh Sleep Quality Index ^e			х		х	х	
Headache Impact Test (HIT-6) e			X		X	X	
SCL-90R Somatization Scale ^e			Х		х	х	
Coping Strategies Questionnaire-Revised ^e			X				
Patient Global Impression of Change ^e					Х	Х	

AUDIT = Alcohol Use Disorders Identification Test; ECG = electrocardiogram; SCL-90 = Symptom Checklist -90R; SF = Short Form; V = Visit

Version 3.0 Page 24 of 25

^a May occur by phone or at a clinic visit, and may be combined with the Screening and Baseline Visit (Visit 0).

Version 3.0 Page 25 of 25

^b If Visit 1 cannot occur within 3 weeks of Visit 0 and the participant is to remain in the study, then Visit 0 will be repeated as an unscheduled visit. The timing of Visits 3-6 and their windows are established from the date of Visit 1.

^c Includes consent for study participation, consent to store biological specimens for future studies, and Health Insurance Portability and Accountability Act statement, if applicable.

^d The first dose of study drug should be taken in the evening of the Day 1.

^e Questionnaires will be distributed at Visit 0 and the participant will return completed questionnaires at Visit 1.
